1. INTRODUCTION

1.1 Study Disease

The standard of care for treatment of early-stage non-small cell lung cancer is surgical resection. However, many patients with this disease have other medical co-morbidities, which may preclude them from undergoing a surgical procedure. Historically, patients with medically inoperable stage I non-small cell lung cancer (*i.e.*, patients who are not surgical candidates due to medical co-morbidities) have been treated with conventionally fractionated radiation therapy, which typically entails treatment with 30 to 35 small doses of radiation given in 2- to 2.5-Gray (Gy) fractions daily over 6 to 8 weeks. Outcomes with this approach have been poor, with local control rates of less than 50% and overall survival of less than 10 to 15% (Dosoretz et al. 1993; Sibley et al. 1998).

Recent advances in image-guided radiation therapy have allowed the safe delivery of hypofractionated radiation therapy (fewer fractions of treatment with a higher dose per fraction). In theory, the use of high doses per fraction may overcome radioresistance and reduce the influence of tumor repopulation (Hall and Giaccia 2006). This technique of using high doses of highly precise, image-guided radiotherapy in only a few fractions of radiotherapy is called stereotactic body radiotherapy (SBRT). SBRT provides patients with medically inoperable lung tumors a promising new treatment, and surgical candidates with a less invasive alternative. Several single-institution series (Onishi, Araki et al. 2004; Grills, Mangona et al. 2011) and phase II studies (Timmerman et al. 2006; Baumann et al. 2009; Fakiris et al. 2009; Timmerman et al. 2010), including a multi-institutional Radiation Therapy Oncology Group (RTOG) study, have demonstrated high local control rates of greater than 80-90% with this approach, and a low risk of severe toxicity (<10%) when patients are appropriately selected.

1.2 Rationale

Perfusion-Based Imaging to Assess Tumor Response

Since SBRT is a novel treatment for early stage lung cancer, predictors of response to treatment and tumor control have not been clearly identified. Radiological evaluation of changes in lung tumor perfusion after the high-dose radiation therapy delivered by SBRT may provide a novel, early predictor of response to treatment. Magnetic resonance imaging (MRI) provides high resolution imaging, and dynamic contrast-enhanced MRI (DCE-MRI) utilizes intravenous gadolinium contrast to evaluate differential enhancement of tumors compared with normal tissue (Tofts et al. 1999; Brasch et al. 2000). Because tumors have increased angiogenesis and vascular permeability, DCE-MRI can be used to distinguish between tumor and normal tissue by assessment of the pharmacokinetic properties of contrast agent uptake in tissues as changes of signal intensity over time, referred to as time-intensity curves. Pharmacokinetic parameters, including the volume transfer constant (K_{trans} ; permeability surface area product per unit volume of tissue), the fractional volume of extravascular extracellular space per volume of tissue (v_e), and the rate constant (k_{ep} ;

CONFIDENTIAL

This document is confidential. Do not disclose or use except as authorized.

efflux rate from extravascular extracellular space back to plasma), can be estimated by fitting a pharmacokinetic model to the actual time–intensity curves obtained from the DCE-MRI.

DCE-MRI has been utilized to provide high resolution spatial imaging of the extent of soft-tissue tumors such as prostate adenocarcinomas (Cheikh, Girouin et al. 2009), and to monitor changes in tumor perfusion in response to therapy (Low, Fuller et al. 2011). Work conducted at Brigham and Women’s Hospital has demonstrated that DCE-MRI can be utilized to assess perfusion in pulmonary nodules, with the addition of motion correction to pharmacokinetic measurements (Tokuda et al. 2011).

DCE-MRI is currently under active study as a potential imaging tool for response assessment after SBRT. A preliminary study using DCE-MRI to assess changes in tumor perfusion after SBRT has been conducted for prostate cancer, and demonstrated decreases in prostate tumor perfusion as early as 2 months after treatment (Low, Fuller et al. 2011). This study demonstrated a 40% decrease in average tumor perfusion (measured by K_{tran}) at 2 months, 75% decrease at 6 months, 82% decrease at 12 months and 87% decrease at 24 months after SBRT. A small series from Cai et al demonstrated that lung tumor perfusion changes after SBRT can be assessed by pulmonary DCE-MRI (Cai, Sheng et al. 2007). Thus, further exploration of this imaging technology in conjunction with SBRT is of great interest.

SBRT Toxicity

Since SBRT is a new technology and novel method of radiation therapy delivery, the long-term toxicity of its use for lung cancers remains to be seen, and the pathophysiology of radiation-induced injury at such high doses is not fully characterized. Of particular concern is the potential development of long-term pulmonary toxicity, which may manifest as radiation pneumonitis or more subacute gradual worsening of dyspnea, hypoxia, and/or decline in pulmonary function test metrics. This spectrum of potentially radiation-related lung injury was observed at a moderate to severe grade (Grade 3-4) in 16% of patients in the phase II RTOG 0236 study (Timmerman, Paulus et al. 2010).

Since the majority of patients receiving SBRT for early stage lung cancer in the United States have significant co-morbidities and/or compromised pulmonary function from underlying lung disease such as chronic obstructive pulmonary disease (COPD), minimizing radiation-induced lung injury is of paramount importance. Prior studies have established the importance of maintaining tight constraints on the volume of lung receiving low to moderate doses of radiation (5 Gy to 20 Gy) to minimize the risk of radiation pneumonitis with both conventionally fractionated radiation therapy (Kwa, Lebesque et al. 1998; Graham, Purdy et al. 1999; Hernando, Marks et al. 2001; Wang, Liao et al. 2006) and SBRT (Barriger et al. 2010; Ong et al. 2010). However, these studies did not distinguish whether the volumes of lung receiving these doses of radiation were functional or not.

Incorporating Functional Lung Imaging into SBRT Treatment Planning

CONFIDENTIAL

This document is confidential. Do not disclose or use except as authorized.

It would be of great interest to utilize functional imaging to guide SBRT treatment planning and to assess treatment response and potential toxicity. Prior studies have attempted to incorporate functional imaging into conventional radiation therapy planning. For instance, studies have demonstrated that functional information from perfusion single positron emission computed tomography (SPECT) can be used to plan radiation therapy (Christian, Partridge et al. 2005; Lavrenkov, Christian et al. 2007; Lavrenkov, Singh et al. 2009) and used to quantify radiation-induced lung injury (Marks, Spencer et al. 1993; Abratt and Willcox 1995; Boersma, Damen et al. 1995; Seppenwoolde, De Jaeger et al. 2004). Furthermore, ventilation/perfusion (V/Q) SPECT has been shown in one study to provide additional useful information for treatment planning beyond perfusion-SPECT (Yuan, Frey et al. 2011). While these nuclear medicine approaches are of interest, they require radioactive tracers that may expose patients to additional radiation, and have inherent limitations in image resolution.

Other groups have studied the role of hyperpolarized helium (He) magnetic resonance imaging (MRI) as a means of incorporating functional imaging into radiation therapy planning. Ireland et al demonstrated in 6 patients that fusion of He-MRI images with planning CT is feasible (Ireland, Bragg et al. 2007; Ireland, Woodhouse et al. 2008), and subsequently demonstrated that incorporating He-MRI images into radiation planning allowed for sparing of functional lung (Bates, Bragg et al. 2009). Cai et al applied this functional imaging technology for SBRT planning using tomotherapy, and demonstrated potential modest sparing of functional lung (Cai, McLawhorn et al. 2011).

In our department, Allen et al studied the role of He-MRI both before and after RT in individuals with locally advanced non-small cell lung cancer, and demonstrated that CT and PET target volumes correlated well, but had poor correlation with He-MRI target volumes defined based on ventilation defects (Allen, Albert et al. 2011). These findings may be related to the decreased spatial resolution seen with He-MRI, and may be one of the key limitations in adapting this modality for radiation treatment planning and assessment of response.

Recently, studies have been published on the potential use of 4D-CT to define regions of functional lung base on voxelized ventilation maps (Guerrero, Sanders et al. 2006; Castillo, Castillo et al. 2010; Nyeng, Kallehauge et al. 2011; Yamamoto, Kabus et al. 2011; Yamamoto, Kabus et al. 2011). These techniques perform deformable image registration between phases of 4D-CT images, and use the density or volume changes as a surrogate for ventilation. Such a technique would be appealing for SBRT because 4D-CT scans are routinely acquired for treatment planning, and no additional imaging studies would be required. However, the physiological accuracy of these novel methods has not yet been thoroughly validated in patient data (Yamamoto, Kabus et al. 2011; Yamamoto, Kabus et al. 2011). Also, the method can only be used to determine lung ventilation, and does not include critical information about perfusion.

Functional Lung Imaging and Radiation-Induced Lung Injury

Another potential application of functional lung imaging includes assessment of radiation-induced lung injury. Preliminary studies by Ireland et al demonstrated that

He-MRI findings can be correlated with CT-based emphysematous changes and also with areas of potential radiation pneumonitis seen on CT (Ireland, Din et al. 2010). Ward et al demonstrated in rat models that after high dose radiation (5 x 8 Gy), He-MRI correlated well with radiation-induced fibrosis (Ward et al. 2004).

Advantages of Perfusion-Based Functional Lung Imaging

Perfusion-based MRI scans have the potential advantages of assessing early tumor response to radiation therapy via changes in tumor perfusion after treatment, higher spatial resolution, improved registration, and patient convenience (routine scan that does not require gas inhalation). Furthermore, these studies may allow assessment of tumor motion while still allowing identification of areas of functional lung, which may allow improved SBRT planning.

Study Rationale

To our knowledge, pulmonary DCE-MRI has not been systematically studied as both an early predictor of tumor response and lung injury and as a SBRT treatment planning tool.

Thus, in this pilot study, we propose to explore the feasibility of pulmonary DCE-MRI in 1) assessing tumor response during and after SBRT treatment; 2) characterizing regions of radiation-induced lung injury after SBRT treatment, and correlating these regions of injury with ventilation changes found on 4D-CT; and 3) identifying regions of functional lung for SBRT treatment planning.

2. OBJECTIVES

2.1 Primary Objective

To determine the feasibility of utilizing pulmonary DCE-MRI to assess for changes in tumor perfusion during SBRT (1-2 days after the first treatment) and post-treatment (at 1-2 weeks and at 3-4 months after SBRT treatment) for stage I NSCLC

2.2 Secondary Objective(s)

- 2.2.1 To evaluate the feasibility of pulmonary DCE-MRI in characterizing acute and subacute (3 months) radiation-induced lung injury after SBRT, and correlate these findings with clinical outcomes
- 2.2.2 To evaluate the feasibility of integrating 4D-CT ventilation imaging with DCE-MRI perfusion imaging in characterizing subacute (3 months) radiation-induced lung injury after SBRT
- 2.2.3 To determine the feasibility of using pulmonary DCE-MRI to identify regions of functional lung for SBRT treatment planning

3. PARTICIPANT SELECTION

3.1 Conditions for Participant Eligibility

- 3.1.1 Participants should preferably have histologically confirmed non-small cell lung cancer, but patients with a clinical and radiographic diagnosis of non-small cell lung cancer who are candidates for stereotactic body radiation therapy may also be eligible.
- 3.1.2 The tumor must be ≥ 1 cm and ≤ 6 cm
- 3.1.3 Participants must have no evidence of nodal involvement (N0) or distant metastases (M0) on staging studies, which may include positron emission tomography (PET), computed tomography (CT), and/or mediastinoscopy.
- 3.1.4 Participants must be age 18 years or older
- 3.1.5 ECOG performance status ≤ 2 (see Appendix A)
- 3.1.6 Participants must be evaluated by radiation oncology and deemed to be a candidate for stereotactic body radiation therapy for NSCLC.
- 3.1.7 Ability to lie still during DCE-MRI which may last for up to 60 minutes
- 3.1.8 Adequate renal function to tolerate intravenous gadolinium contrast injection (estimated glomerular filtration rate ≥ 45 mL/min/1.73 m² prior to initial DCE-MRI and estimated glomerular filtration rate ≥ 30 mL/min/1.73 m² for subsequent DCE-MRI scans).
- 3.1.9 Ability to understand and the willingness to sign a written informed consent document

3.2 Conditions for Participant Ineligibility

- 3.2.1 Primary tumor size > 6 cm
- 3.2.2 Prior thoracic radiotherapy directed to the ipsilateral lung or prior surgical wedge resection in the involved lobe
- 3.2.3 An implanted pacemaker or cardiac defibrillator
- 3.2.4 Contraindications to receiving intravenous gadolinium contrast injection including prior allergic reaction and/or chronic renal insufficiency (estimated glomerular filtration rate < 45 mL/min/1.73 m² prior to initial DCE-MRI and estimated glomerular filtration rate < 30 mL/min/1.73 m² for subsequent DCE-MRI scans).

CONFIDENTIAL

This document is confidential. Do not disclose or use except as authorized.

- 3.2.5 Any contraindication to undergoing MRI (e.g., pacemakers, cochlear implants, shrapnel injuries, or other types of metal or electric devices in the body, severe claustrophobia, cataract surgery with certain ocular implants—see below)
- 3.2.5.1 The following ocular implant models from Bausch & Lomb are considered unsafe for MRI: Intraocular Lens, Models 12A, 12P, 12S, 24P, 31P, 42P, 61P, 71, 71B, 71M, 71P, 71PC, 71R, 75M, 75P, EXP D
- 3.2.6 Uncontrolled intercurrent illness including, but not limited to ongoing or active infection, unstable angina pectoris, cardiac arrhythmia, or psychiatric illness/social situations that would limit compliance with study requirements
- 3.2.7 Pregnant women are excluded from this study because radiotherapy has the potential for teratogenic or abortifacient effects. Because there is an unknown but potential risk of adverse events in nursing infants secondary to treatment of the mother with radiotherapy, breastfeeding should be discontinued if the mother is treated with radiotherapy. These potential risks may also apply to other agents used in this study.

3.3 Inclusion of Women, Minorities and Other Underrepresented Populations

Women, minorities and other underrepresented populations are all at risk to develop non-small cell lung cancer, with smoking as the critical risk factor for the disease. Socioeconomically-deprived populations tend to have higher rates of smoking, and therefore it is possible this study will be more likely to enroll these individuals. However, the proposed MRI studies and the standard SBRT treatment will not have a differential effect on these populations. The eligibility criteria should not substantially differentially affect their enrollment in the trial, although some minority populations are more likely to have renal failure, which may preclude them from the trial.

4. PRETREATMENT EVALUATIONS/MANAGEMENT

4.1 Screening and Non-Study Pretreatment Evaluations

This visit will be performed within 4 weeks prior to the initiation of the stereotactic body radiation therapy. Potential participants will be evaluated for their performance status, and interviewed for their medical history and concomitant medications, followed by a physical examination. Vital signs (oral body temperature, heart rate and blood pressure) will be measured. Baseline blood tests will be performed. In addition, a blood pregnancy test will be performed for females of child-bearing potential.

Eligibility in the context of the study inclusion and exclusion criteria will be evaluated by the investigator. Potential participants will be asked to sign the informed consent and will be assigned a participant study number in a sequential order. If participants do not have a FDG PET/CT scan within 10 weeks and a pulmonary function test within 6

CONFIDENTIAL

This document is confidential. Do not disclose or use except as authorized.

months prior to the scheduled date of initiation of SBRT, they will undergo a repeat FDG PET/CT and/or pulmonary function test at the study site, as part of standard of care procedures.

5. REGISTRATION PROCEDURES

5.1 General Guidelines for DF/HCC and DF/PCC Institutions

Institutions will register eligible participants in the Clinical Trials Management System (CTMS) OnCore. Registrations must occur prior to the initiation of protocol therapy. Any participant not registered to the protocol before protocol therapy begins will be considered ineligible and registration will be denied.

An investigator will confirm eligibility criteria and a member of the study team will complete the protocol-specific eligibility checklist.

Following registration, participants may begin protocol therapy. Issues that would cause treatment delays should be discussed with the Overall Principal Investigator (PI). If a participant does not receive protocol therapy following registration, the participant's registration on the study must be canceled. Registration cancellations must be made in OnCore as soon as possible.

5.2 Registration Process for DF/HCC and DF/PCC Institutions

DF/HCC Standard Operating Procedure for Human Subject Research Titled *Subject Protocol Registration* (SOP #: REGIST-101) must be followed.

6. STUDY DESIGN

6.1 Design/Study Type

This study is a non-randomized single-arm prospective study evaluating the feasibility of utilizing pulmonary DCE-MRI to assess for treatment response during and after SBRT and to guide SBRT treatment planning. The primary objective of this study is to test the feasibility of using pulmonary DCE-MRI scans to assess for changes in tumor perfusion during treatment (1-2 days after the first SBRT fraction) and after SBRT treatment (at 1-2 weeks and 3 months after SBRT) for early stage NSCLC. The study will have a two-stage design with a preliminary assessment of feasibility after enrollment of 7 eligible participants (see Section 15.1, Statistical Considerations). If the feasibility criteria are met, a total of 20 eligible participants will be enrolled.

Secondary objectives include determining the feasibility of 1) using pulmonary DCE-MRI to assess for lung injury 3 months after SBRT; 2) correlating ventilation changes

as measured by 4D-CT with the perfusion changes measured with DCE-MRI at 3 months after SBRT; and 3) incorporating pulmonary DCE-MRI into SBRT treatment planning.

The radiation therapy itself, which will be delivered using SBRT techniques, is not investigational and will be delivered per the standard of care. While one of the secondary study objectives is to determine the feasibility of incorporating pulmonary DCE-MRI into SBRT treatment planning, participants on this pilot study will **NOT** have their SBRT treatment planning influenced or guided by the results of the pretreatment pulmonary DCE-MRI, and will be treated per the standard of care, which includes utilizing free-breath contrast-enhanced CT, 4D-CT and PET/CT for treatment planning.

The research specific pulmonary DCE-MRI and post-treatment 4D-CT scans will be paid for by the study. The patient and/or insurance company will be responsible for the visits, work-up (e.g. PET-CT and PFTs), SBRT treatment planning (including planning 4D-CT), treatment delivery, and post-treatment surveillance studies (e.g. PET-CT and PFTs) performed as part of the patient's standard clinical care, and not for research purposes.

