15. STATISTICAL CONSIDERATIONS

15.1 Study Design/Endpoints

The primary objective of this study is to determine the feasibility of utilizing pulmonary DCE-MRI to assess changes from baseline in tumor perfusion during SBRT treatment

CONFIDENTIAL

This document is confidential. Do not disclose or use except as authorized.

(after 1 fraction of SBRT), and 1-2 weeks and 3-4 months after completion of SBRT treatment for stage I NSCLC. **Feasibility (success) is defined as successfully enrolling patients, processing the pulmonary DCE-MRI data, and observing an analyzable change in tumor perfusion between the pre-treatment DCE-MRI and any of the DCE-MRI scans during SBRT (after 1 fraction) or after completion of SBRT treatment. Analyzable change will be defined as a 20% change in tumor perfusion. A recent publication by Ng et al reported the rate of reproducibility of DCE-MRI parameters was between 10-20% (Ng, Raunig et al. 2010), and we have chosen the upper limit of this range to be conservative.**

A total of 20 participants with stage I NSCLC will be enrolled on this study, and a two-stage design will be used. Seven eligible participants in the first stage and 10 eligible participants in the second stage will be accrued. To allow for participants that are unable to complete scans and/or are ineligible to continue on the study, 3 additional participants will be accrued, so up to 8 participants in stage I and 12 participants in stage II will be accrued to this study. If at least 5 successes are observed among the 7 eligible participants in the first stage, up to an additional 12 participants (10 eligible) will be entered. If 14 or more successes are observed among the 17 eligible participants, utilizing pulmonary DCE-MRI to assess changes in tumor perfusion will be considered feasible for this group. With this design, there is a 90% probability of declaring the pilot study feasible if the true feasibility rate is 90%, and a 10% probability of declaring the DCE-MRI worthy of further study if the true feasibility rate is 65%. With 17 eligible participants, we have 90% power to detect a difference of 0.75 standard deviation in the change of tumor perfusion from baseline (prior to SBRT treatment) to post treatment (either right after SBRT treatment or 3-4 months after SBRT treatment) using a 0.1 level two-sided Wilcoxon signed-rank test.

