15.2 Sample Size/Accrual Rate

Twenty participants will be enrolled in this pilot study. We estimate that approximately 20 patients a year would meet the eligibility criteria for enrollment on this study. Assuming that one third of the eligible patients would consent to enrolling on the study, the accrual rate would be 6 patients per year and accrual will be complete within 3.5 years. After the last post-treatment DCE-MRI scan (3-4 months after treatment), participants will be off study, but will continue to undergo follow-up per standard care. Thus, the study will be complete after 4 years.

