15.5 Reporting and Exclusions

- 15.5.1 **Evaluation of toxicity.** All participants will be evaluable for toxicity from the time of their first DCE MRI.
- 15.5.2 **Evaluation of primary endpoint.** All participants who undergo a pre-treatment DCE-MRI and at least one post-treatment DCE-MRI will be included in the study.

CONFIDENTIAL

This document is confidential. Do not disclose or use except as authorized.

15.5.3 **Stopping Rules.** There is no experimental component to the radiation treatment or radiological imaging (both SBRT and the DCE-MRI are utilized in routine clinical care). However, the study will be stopped if preliminary study results determine that it is not feasible to utilize DCE-MRI to achieve any of the primary or secondary objectives including assessing tumor perfusion (primary objective) and lung injury or assisting SBRT treatment planning.

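### Section 6.1 gives 20 eligible participants, but Section 15.1 plans 17 eligible of up to 20 enrolled and writes its go/no-go rule only for 7 and 17

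*Combined protocol and SAP*

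**What the plan says.** Section 6.1 places the interim look after 7 eligible participants, sends the reader to Section 15.1 for the design, and continues: "If the feasibility criteria are met, a total of 20 eligible participants will be enrolled".

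Section 15.1 gives a different eligible total: "Seven eligible participants in the first stage and 10 eligible participants in the second stage will be accrued". It adds 3 participants to cover those who cannot complete scans or cannot continue, which makes up to 8 in stage I and 12 in stage II. After at least 5 successes among 7, "up to an additional 12 participants (10 eligible) will be entered". The final rule begins "If 14 or more successes are observed among the 17 eligible participants". The stated probabilities are 90% of declaring feasibility at a true rate of 90%, and 10% at a true rate of 65%.

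Two sentences give 20 as a flat number rather than a ceiling: "A total of 20 participants with stage I NSCLC will be enrolled on this study" in 15.1 and "Twenty participants will be enrolled in this pilot study" in 15.2.

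On who counts, 15.1 allows a success on "any of the DCE-MRI scans during SBRT (after 1 fraction) or after completion of SBRT treatment". Section 15.5.2 says: "All participants who undergo a pre-treatment DCE-MRI and at least one post-treatment DCE-MRI will be included in the study". Sections 7.2 and 13.2 list the during-treatment scan separately from the two post-treatment scans.

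**The concern.** The eligible count in 6.1 does not match the design it points to. In 6.1 the interim figure of 7 is the eligible count of 15.1, not its stage I ceiling of 8. On one meaning of the word, 7 should pair with 17, not 20.

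The mismatch touches the primary go/no-go decision. The 3 extra places are an allowance for loss. If 20 are enrolled and fewer than 3 are lost, 18 to 20 participants are evaluable. Section 15.5.2 sets no cap, and 15.1 has no rule for those numbers. The decision set or the cut-off would then be chosen after the data are seen.

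The scan requirement is a second, separate mismatch about who is evaluable. A participant with only a baseline and a during-SBRT scan can be a success under 15.1 but falls outside 15.5.2 read literally. This can happen: Section 13.4 cancels a scan when renal function is too low, and 15.1 lets stage II drop uninformative time points. If only the during-SBRT scan were kept, 15.5.2 read literally would exclude every stage II participant.

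**Working it through.** **Inputs (Section 15.1).** Stage I: n1 = 7, continue if X1 ≥ 5. Stage II: n2 = 10, feasible if X1 + X2 ≥ 14. True rates: 0.65 and 0.90.

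**Accrual arithmetic.** 7 + 10 = 17; 17 + 3 = 20; 8 + 12 = 20. Section 15.1 is internally consistent with 17 eligible of up to 20 accrued.

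**The plan's own figures.** P(feasible) = Σ over x = 5, 6, 7 of P(X1 = x) × P(X2 ≥ 14 − x), with X1 ~ Bin(7, p) and X2 ~ Bin(10, p).

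- p = 0.65: 0.2985 × 0.0860 + 0.1848 × 0.2616 + 0.0490 × 0.5138 = 0.0257 + 0.0483 + 0.0252 = **0.0992** (stated 10%).
- p = 0.90: 0.1240 × 0.7361 + 0.3720 × 0.9298 + 0.4783 × 0.9872 = 0.0913 + 0.3459 + 0.4722 = **0.9094** (stated 90%).

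Both reproduce. The Wilcoxon statement in 15.1 also rests on 17: with 0.75 SD and a two-sided 0.10 level, simulated power is 0.893, against 90% stated.

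**Can 20 simply replace 17?** All cut-off pairs with a stage I of 7 or 8 were examined against error ≤ 10% and power ≥ 90%.

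- Power cannot exceed the chance of passing stage I. Requiring 6 of 7 caps it at 0.3720 + 0.4783 = 0.850. Requiring 7 of 8 caps it at 0.813. So only stage I cut-offs up to 5/7 or 6/8 remain.
- Total of 19: a final cut-off of 16 or more has power of at most 88.5%. A final cut-off of 15 or less has error of at least 13.8% (5/7) or 13.1% (6/8).
- Total of 20: a final cut-off of 17 or more has power of at most 86.7%. A final cut-off of 16 or less has error of at least 11.0% (5/7) or 10.5% (6/8).

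No pair meets both targets at 19 or 20.

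**If more than 17 are evaluable.** Compare two defensible rules, with stage I decided as 5/7: (A) the first 17, at least 14; (B) all N, with an adjusted cut-off r. For N = 18 and r = 15 they differ only when the first 17 hold exactly 14 successes and the 18th is a failure. The number of arrangements with X1 ≥ 5 and 14 successes is 21×10 + 7×45 + 1×120 = 645. So P(differ) = 645 × p^14 × (1−p)^3 × (1−p), which is 0.0233 at 0.65 and 0.0148 at 0.90. The other rows come from the same enumeration. The 77.5% column is an assumption, the midpoint (65 + 90)/2.

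| Rule B | 65% | 77.5% | 90% |
|---|---|---|---|
| 15/18 | 2.3% | 4.7% | 1.5% |
| 16/19 | 4.2% | 9.0% | 3.1% |
| 16/20 | 5.0% | 11.5% | 4.1% |
| 17/20 | 5.6% | 13.1% | 4.8% |

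**How often this arises.** The documents give no loss rate. As an illustration only, suppose all 20 are accrued regardless and each is lost independently. P(more than 17 evaluable) is then about 0.40 at 15% loss (the 3/20 allowance) and 0.93 at 5% loss. At 15% loss, P(18), P(19) and P(20) are 0.229, 0.137 and 0.039. Overall disagreement at a true 65%, using 15/18, 16/19 and 17/20, is 0.229 × 0.0233 + 0.137 × 0.0416 + 0.039 × 0.0558 ≈ 1.3%. If accrual stops at 17 eligible, it is near zero.

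**The case against.** The best defence is that only one word is wrong. Section 15.1 is complete and correct, 6.1 refers to it, and the total of 20 agrees across 6.1, 15.1 and 15.2. Section 15.1 says why the 3 extra places exist and uses ceiling language for both stages. It is most naturally read as replacement slots, with accrual ending at 17 eligible. On that reading, only the label in 6.1 is wrong on the count. This stands in large part and limits the weight of the point. It does not remove it: the same section and 15.2 also state 20 as a flat number, 15.5.2 sets no cap, and overshoot is nowhere addressed.

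A reader might infer something stronger: that the study would carry 14 as its cut-off to 18, 19 or 20 participants and so inflate its error, or that stage I would be judged on 8. The documents support neither. No passage prescribes 14 beyond 17, and both 6.1 and 15.1 tie the interim look to 7 eligible.

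It can also be said that the scan mismatch concerns evaluability, not 17 versus 20. That is correct. It is a separate wording error, included here because both affect the set to which the rule applies, and it does not add to the weight of the 6.1 error.

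**Conclusion.** Wrong as written, minor in weight. The 20 eligible participants in 6.1 contradict the 17 in 15.1. The go/no-go rule is defined and correct at 7 and 17 (error 9.9%, power 90.9%), and 20 cannot be substituted, because no cut-off pair with a stage I of 7 or 8 meets both stated targets at 19 or 20.

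The practical effect is conditional. If more than 17 are evaluable, two reasonable readings of the rule disagree in about 1.5% to 5.6% of trials at the design rates, and in 4.7% to 13.1% at an assumed true rate of 77.5%. These figures assume independent outcomes and a stage I decision on the first 7. Their frequency in practice depends on a loss rate that the documents do not give. It should not be inferred that the sample-size calculation is faulty or that the stated error rate is inflated.

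Section 15.5.2 also needs correction, since read literally it can exclude participants whom 15.1 counts as successes. The stakes are limited by the setting: under 6.1 this is a single-arm pilot whose imaging does not influence treatment.

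**What to change.** 1. Section 6.1: change the total to *17 eligible participants (up to 20 enrolled)*.
2. Sections 15.1 and 15.2: write *up to 20* wherever 20 is given as the number enrolled.
3. Section 15.5.2: replace the post-treatment scan requirement with *at least one later DCE-MRI (during or after SBRT)*.
4. Section 15.1: add that the stage I and final decisions use the first 7 and first 17 evaluable participants in registration order. Define evaluable as eligible under Section 3, with a baseline and at least one later DCE-MRI acquired. Scans that cannot be processed, or that show less than a 20% change, count as failures. Further evaluable participants enter only a sensitivity estimate of the feasibility rate, with an exact 95% confidence interval. The Wilcoxon analysis of perfusion change uses all evaluable participants.

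Use *evaluable* for this set, so that *eligible* keeps its Section 3 meaning. Registration order is one reasonable choice rather than one the documents dictate; what matters is that it is fixed in advance. If 20 eligible is truly intended, the rule and its probabilities must be rewritten, not relabelled.

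Cost: a few phrases and a short added paragraph, with no added participants or scans. The downside is that up to 20 − 17 = 3 evaluable participants would not count in the formal decision.
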